15.5 Handling of Missing Data

[figure not shown]
The AAS and BAS do not include any imputed values. Although missing data will occur, the influence of the missing data is expected to be minimal.

15.6 Multiplicity

A total of six hypothesis tests will be conducted to address the primary and secondary objectives of the study.

A combination of gate-keeping and Bonferroni adjustment strategies will be employed to control the overall type I error rate. The hypothesis tests and the testing order (multiplicity adjustment) are outlined in Figure 15-1.

Figure .15-1 Multiple Testing Strategy

15.7 Safety Analysis

Adverse Events

All information obtained on AEs will be displayed by treatment and subject.

The number and percentage of all ocular adverse events, including secondary surgical interventions (SSIs) for either eye, will be tabulated by preferred term with a breakdown by treatment and implanted eye. An eye with multiple ocular AEs of the same preferred term is only counted once toward the total of this preferred term.

The number and percentage of all adverse events will also be tabulated with a breakdown by treatment.

Device Deficiencies

The number and percentage of all device deficiencies will be tabulated with a breakdown by treatment and implanted eye. A listing of all device deficiencies will also be provided.

IOL Observations

The number and percentage of all IOL observations will be tabulated with a breakdown by treatment and implanted eye.

Subjective Posterior Capsule Opacification

The number and percentage of eyes within each category of subjective posterior capsule opacification will be tabulated with a breakdown by treatment and implanted eye.

Posterior Capsulotomy

The number and percentage of eyes with posterior capsulotomy will be tabulated with a breakdown by treatment and implanted eye.

Other Safety Assessments

All other safety assessments (including intraocular pressure, slit lamp examination, IOL position change, fundus visualization, dilated fundus examination and surgical problems) will be summarized. Number and percentage will be presented for categorical variables and descriptive statistics including mean, standard deviation, minimum and maximum will be presented for continuous variables.

15.8 Interim Analyses

An interim analysis will be performed when all subjects complete Visit 3A (20-40 days post 2nd eye implantation) in order to support the study publication plan of the test articles for near, intermediate and distance visual acuity, contrast sensitivity, defocus curves and adverse events. The interim analysis results will be distributed to a limited audience to limit potential bias in Visit 4A assessments. The clinical trial team with the exception of the Brand Lead will be masked to the interim analysis results.

15.9 Adaptive Study Design

Not applicable.

15.10 Sample Size Justification

The multiplicity adjustment strategy is outlined in Figure 15.-1. Sample size estimations are based on the minimum sample size needed to achieve 90% power for all hypothesis tests. A type I error rate of 2.5%, one-sided, is used for calculations to account for simultaneous testing in Gate 2 (see Figure 15-1).

Assuming a dropout rate of 5%, approximately 160 subjects will be bilaterally implanted in 1:1 allocation ratio (test: control) to achieve at least 152 subjects who complete the study. With 152 subjects (76 per group) there is 98% probability that an upper one-sided 97.5% confidence limit on the difference (test-control) in visual acuity will be less than 0.1 logMAR, assuming the mean difference of 0.0 logMAR and a common standard deviation of 0.16 logMAR, the maximum observed for binocular uncorrected distance, intermediate and near visual acuity in a previous Alcon study (C-06-40, ReSTOR +3.0 D IOL).

Also, with 76 subjects per group, there is more than 90% power to detect a difference of 0.09 logMAR (4.5 letters) between means in a two sample t-test conducted at a 2.5% chance of a Type I error and assuming a standard deviation of 0.16 logMAR for binocular uncorrected distance, intermediate and near visual acuity.

16 ADMINISTRATIVE PROCEDURES

16.1 Regulatory and Ethical Compliance

This clinical trial will be conducted in accordance with the principles of the Declaration of Helsinki, and in compliance with ISO 14155:2011 Clinical investigation of medical devices for human subjects – Good clinical practice, Code of Federal Regulations (CFR), and laws and regulations of foreign countries, whichever affords greater protection to subjects. The trial shall also be conducted in accordance with the Sponsor’s Standard Operating Procedures (SOPs) and all other applicable regulations. The Investigator and all clinical trial staff will conduct the clinical trial in compliance with this protocol. The Investigator will ensure that all personnel involved in the conduct of the clinical trial are qualified to perform their assigned duties through relevant education, training, and experience.

16.2 Informed Consent Procedures

Voluntary informed consent will be obtained from every subject prior to the initiation of any screening or other clinical trial-related procedures. The Investigator must have a defined process for obtaining consent. Specifically, the Investigator, or designee, will explain the clinical trial to each potential subject and the subject must indicate voluntary consent by signing and dating the approved informed consent form. The subject must be provided an opportunity to ask questions of the Investigator, and if required by local regulation, other qualified personnel. The Investigator must provide the subject with a copy of the consent form written in a language the subject understands. The consent document must meet all applicable local laws and will provide subjects with information regarding the purpose, procedures, requirements, and restrictions of the clinical trial, along with any known risks and potential benefits associated with the investigational product, the available compensation, and the established provisions for maintaining confidentiality of personal, protected health information. Subjects will be told about the voluntary nature of participation in the clinical trial and will be provided with contact information for the appropriate individuals should questions or concerns arise during the clinical trial. The subject also will be told that their records may be accessed by appropriate authorities and Sponsor-designated personnel. The Investigator must keep the original, signed copy of the consent and must provide a duplicate copy to each subject.

16.3 Responsibilities of the Investigator and IRB/IEC

Before clinical trial initiation, this protocol, the informed consent form (and assent form, if applicable), any other written information provided to subject, and any advertisements planned for subject recruitment must be approved by an Institutional Review Board /

Independent Ethics Committee (IRB/IEC). A master list of IRBs/IECs for this clinical trial can be found in the Trial Master File. The Investigator must provide documentation of IRB/IEC approval to the Sponsor. The approval must be dated and must identify the applicable protocol, amendments (if any), informed consent form, assent form (if any), all applicable recruiting materials, written information for subjects, and subject compensation programs. The IRB/IEC must be provided with a copy of the Investigator's Brochure, any periodic safety updates, and all other information as required by local regulation and/or the IRB/IEC. At the end of the clinical trial or in the case of early termination, the Investigator will notify the IRB/IEC of the clinical trial's final status. Finally, the Investigator will report to the IRB/IEC on the progress of the clinical trial at intervals stipulated by the IRB/IEC.

16.4 Sponsor and Monitoring Responsibilities

The Sponsor will designate a monitor to conduct the appropriate site visits at the appropriate intervals. The clinical investigation will be monitored, following the Protocol Monitoring Plan, to ensure that: the rights and well-being of the subjects are protected; the reported data are accurate, complete, and verifiable from the source documents; the equipment used to assess variables in the clinical investigation is maintained and calibrated per manufacturer instructions and Sponsor requirements; the study is conducted in compliance with the current approved protocol (and amendment[s], if applicable), with current Good Clinical Practice (GCP), and with applicable regulatory requirements.

All investigative sites will have a site initiation. Monitoring will be conducted periodically while the clinical study is ongoing. Monitoring methods may include site visits, telephone, written and fax correspondence. The assigned CSM will contact each site at appropriate intervals. The Lead Clinical Site Manager (LCSM) will determine the frequency of site visits. Closeout visits will take place after the last visit of the last subject.

16.5 Regulatory Documentation and Records Retention

Essential documents must be retained by the investigator in compliance with the medical device directive and its local transposition as well as other applicable national and international regulations. The investigator(s)/institution(s) must comply with record retention stipulations outlined in the Clinical Study Agreement. Additionally the Investigator will be supplied with further instruction at study completion.

16.6 Clinical Trial Results

The Investigator will notify the accredited ethics committee of the end of the study as required by the ethics committee. The end of the study is defined as database lock. In case the

study is ended prematurely, the Investigator will notify the accredited ethics committee, including the reasons for the premature termination. Within one year after the end of the study, the Investigator/sponsor will submit a final study report with the results of the study, including any publications/abstracts of the study, to the accredited ethics committee as required.

**Job Notes:**

This is the original (Version 1.0) Statistical Analysis Plan for this study. This version of the Statistical Analysis Plan is based on Version 2.0 of the study protocol.

## **Executive Summary:**

### **Key Objectives:**

The key objective is to demonstrate non-inferiority of the TFNT00 IOL to the 839MP IOL in mean photopic binocular uncorrected intermediate (60 cm) visual acuity (UCIVA) at Visit 4A (120-180 days post 2nd eye implantation).

### **Decision Criteria for Study Success:**

The study will be considered a success if, at least, the primary objective is met.

A two-sided 90% confidence interval using repeated measures analysis of variance will be generated for the difference in mean photopic binocular uncorrected intermediate (60 cm) visual acuity of TFNT00 IOL group minus 839MP IOL group based on least squares means. Non-inferiority of the TNFT00 IOL will be concluded if the upper bound of the interval is less than the margin, 0.1 logMAR.

4.6 Subgroup Analyses and Effect of Baseline Factors..... 18

4.7 Interim Analysis for Effectiveness ..... 19

5 Safety Analysis Strategy ..... 19

5.1 Safety Assessments ..... 19

5.2 Safety Hypotheses ..... 19

5.3 Statistical Methods for Safety Analyses ..... 20

5.3.1 Adverse Events ..... 20

5.3.2 Device Deficiencies ..... 21

5.3.3 Surgical Problems ..... 21

5.3.4 Intraocular Pressure ..... 21

5.3.5 Slit Lamp Examination ..... 22

5.3.6 IOL Observations ..... 22

5.3.7 IOL Position Change ..... 22

5.3.8 Subjective Posterior Capsule Opacification ..... 22

5.3.9 Posterior Capsulotomy ..... 22

5.3.10 Fundus Visualization ..... 22

5.3.11 Dilated Fundus Examination ..... 23

5.4 Interim Analysis for Safety ..... 23

6 Analysis Strategy for Other Endpoints ..... 23

7 Sample Size and Power Calculations ..... 23

[figure not shown]
[figure not shown]
8 References ..... 24

9 Revision History ..... 24

█ [REDACTED] 24

11 Appendix ..... 25

# 1 Study Objectives and Design

## 1.1 Study Objectives

### *Primary Objective:*

To demonstrate **non-inferiority** of ACRYSOF IQ PanOptix presbyopia-correcting IOL Model TFNT00 to the AT Lisa tri IOL Model 839MP in mean photopic binocular uncorrected **intermediate** (60 cm) visual acuity at Visit 4A

### *Secondary Objectives:*

1. To demonstrate **superiority** of ACRYSOF IQ PanOptix IOL versus the AT LISA tri IOL Model 839MP in mean photopic binocular uncorrected **intermediate** (60 cm) visual acuity at Visit 4A
2. To demonstrate **non-inferiority** of ACRYSOF IQ PanOptix IOL versus the AT LISA tri IOL Model 839MP in mean photopic binocular uncorrected **distance** (4 m) visual acuity at Visit 4A
3. To demonstrate **non-inferiority** of ACRYSOF IQ PanOptix IOL versus the AT LISA tri IOL Model 839MP in mean photopic binocular uncorrected **near** (40 cm) visual acuity at Visit 4A
4. To demonstrate **superiority** of ACRYSOF IQ PanOptix IOL versus the AT LISA tri IOL Model 839MP in mean photopic binocular uncorrected **near** (40 cm) visual acuity at Visit 4A
5. To demonstrate **superiority** of ACRYSOF IQ PanOptix IOL versus the AT LISA tri IOL Model 839MP in mean photopic binocular uncorrected **distance** (4 m) visual acuity at Visit 4A
6. To **characterize** the binocular defocus curve profiles, contrast sensitivity and patient satisfaction with ACRYSOF IQ PanOptix IOL versus the AT LISA tri IOL Model 839MP at Visit 4A

## 1.2 Study Description

[figure not shown]
This study is a prospective, multi-center, postmarket trial comparing the visual function of 2 presbyopia-correcting trifocal IOLs following bilateral implantation. Both trifocal IOLs are

commercially available in the countries where the study is being conducted. Enrolled subjects will attend a total of 9 visits (6 postoperative) approximately over a 7 month period.

An overview of the study design is depicted in Figure 1-1.

The schedule of visits is included as Table 11-1 in the appendix.

**Figure .1-1 Study Design**

### 1.3 Randomization

Post consent, the EDC system will assign the subject number. Within 10 business days of surgery, qualified subjects will be randomized, in a 1:1 ratio, to either the TFNT00 or 839MP IOL.

Randomization will be stratified by study site to ensure a balance of study treatment allocations within each investigational site.

## 1.4 Masking

In order to reduce bias, the observer (ie, study technician assessing primary and secondary endpoint data) and the subject will be masked to the treatment assignment for the duration of his/her trial participation, and will be provided with his/her permanent implant card upon study exit.

In addition, all Alcon personnel involved with planning, execution and analysis of the study will be masked with regard to treatment assignment while the study is in progress. The exception will be the Brand Lead who will receive unmasked interim analysis results.

## 1.5 Interim Analysis

An interim analysis of the data will be performed when all subjects complete Visit 3A (20-40 days post 2nd eye implantation) in order to support the study publication plan of the test articles for near, intermediate and distance visual acuity, contrast sensitivity, defocus curves and adverse events. The interim analysis results will be distributed to a limited audience to limit potential bias in Visit 4A assessments. The clinical trial team with the exception of the Brand Lead will be masked to interim analysis results.

## 2 Analysis Sets

### 2.1 Effectiveness Analysis Sets

The all-implanted analysis set (AAS) will include all eyes with successful test or control article bilateral implantation.

The best-case analysis set (BAS) will include all eyes successfully implanted with the test or control article that had at least one postoperative visit, and with no macular degeneration at any time, and no major protocol deviations. Subjects who become pregnant at any time during the study will also be excluded from the BAS.

The primary analysis set for performance analyses will be the AAS for all performance endpoints, except for binocular defocus and contrast sensitivity for which it will be considered supportive. The BAS will be the primary set for binocular defocus and contrast sensitivity. Additional supportive analyses may be conducted using the BAS or AAS.

All effectiveness analyses will be conducted according to actual test or control article implanted.

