		Visit 00 Day 0 1 st Eye Implantation	Visit 1 1-2 Day Post 1 st Eye Implantation	Visit 2 7-14 Days Post 1 st Eye Implantation	Visit 00A 2-21 Days Post Visit 00 2 nd Eye Implantation	Visit 1A 1-2 Day Post 2 nd Eye Implantation	Visit 2A 7-14 Days Post 2 nd Eye Implantation	Visit 3A 20-40 Days Post 2 nd Eye Implantation	Visit 4A ¹ 120-180 Days Post 2 nd Eye Implantation	UNSV ² N/A
Contrast Sensitivity (Binocular)										
• Mesopic without Glare								X	X	
• Mesopic with Glare								X	X	
• Photopic without Glare								X	X	
• Photopic with Glare								X	X	
Slit-Lamp Examination (Including IOL Observations)	X		X	X		X		X	X	X
IOL Position Change			X	X		X		X	X	X
Subjective PCO			X	X		X		X	X	X
Posterior Capsulotomy (Report if performed)			X	X		X		X	X	X
Fundus Visualization								X	X	

Activity	Bin-ocular	1 st Eye			2 nd Eye			Binocular		Mon-ocular
	Visit 0	Visit 00	Visit 1	Visit 2	Visit 00A	Visit 1A	Visit 2A	Visit 3A	Visit 4A ¹	UNSV ²
	Day -60 to 0 Preoperative	Day 0 1 st Eye Implantation	1-2 Day Post 1 st Eye Implantation	7-14 Days Post 1 st Eye Implantation	2-21 Days Post 2 nd Eye Implantation Visit 00	1-2 Day Post 2 nd Eye Implantation	7-14 Days Post 2 nd Eye Implantation	20-40 Days Post 2 nd Eye Implantation	120-180 Days Post 2 nd Eye Implantation	N/A
Dilated Fundus Examination	X							X	X	X
IOP	X		X	X		X	X	X	X	X
Adverse Events (Including SSI)	X	X	X	X	X	X	X	X	X	X
Device Deficiencies		X	X	X	X	X	X	X	X	X

¹ If a subject exits early, the Visit 4A procedures should be performed at the last available visit, if at all possible.

² UNSV assessments listed are recommended. Only complete assessments required per the PI medical judgment.

³ Women of child-bearing potential only

⁵ Within 10 business days of treatment (Visit 00).

⁶ Data is reported in EDC at the surgical visit, but may be collected at a previous visit.

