10.3 Exclusion Criteria During Surgery

Below is a list of criteria that when occurring prior to IOL implantation prevent the study lens from being implanted. This is true for both eyes.

19. Any other additional procedures during the phacoemulsification and IOL implant due to intraoperative complications that require further intervention (including but not limited to posterior capture rupture, vitreous loss, zonular dehiscence that may make the IOL implant less stable, etc.)
20. Uncontrolled intraocular pressure

21. Significant anterior chamber bleeding
22. Excessive iris mobility
23. Mechanical or surgical manipulation required to enlarge the pupil prior to or at IOL implantation (pupil size must be at least 4.5 mm or larger just prior to implantation)
24. Capsulorhexis tears or any areas of “can-opener” capsulotomy
25. Unrecognized (pre-existing but discovered during surgery) ocular conditions or complications in which the IOL stability could be compromised, including zonular weakness
26. Zonular or Capsule rupture
27. Intended IOL haptic placement other than bag-bag

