12.1.2 Operative Visit (Visit 00/00A)

Visit 00: Day 0, Monocular 1st Eye

Visit 00A: 2-21 Days Post 1st Eye Implantation, Monocular 2nd Eye

Below is a list of study procedures to be undertaken at Visit 00 and Visit 00A. It is recommended that procedures are performed in the order described below unless otherwise stated. Activities involving multiple delegated staff members may be performed in parallel. All assessments must be documented in source documentation and case report forms (if applicable).

Note: the Visit 00A window may overlap with other study visit windows (eg, Visit 1, Visit 2). In this case, both visits may be conducted on the same day at the discretion of the Investigator.

1. In preparation for the operative visit, randomize the subject. Randomization should be performed within 10 business days of Visit 00. It is recommended that subjects are contacted prior to randomization to 1) confirm willingness to continue trial participation, and 2) confirm scheduled surgical date and time.
2. Prior to treatment, review inclusion/exclusion criteria and ensure the subject has been properly consented for participation in the trial.
3. Document any changes to ocular and non-ocular concomitant medications.
4. Record operative eye.
5. Prepare subject for surgery in accordance to site specific operating procedures.
[Operative Eye Only, Monocular]
6. Perform surgery and implantation with the randomized IOL.
[Operative Eye Only, Monocular]
7. Record any surgical problems, complications, or other procedures that occur during surgery. Other procedures include those performed outside of routine cataract surgery.
Note: Other planned procedures at the time of surgery are exclusionary.
[Operative Eye Only, Monocular]
8. Record the lens information that is located on the IOL sticker. Both successful and aborted (if applicable) test article information should be recorded.
[Operative Eye Only, Monocular]
9. Record any adverse events including SSIs.
Note: Serious adverse events (SAEs) including SSIs must be entered into EDC within 24 hours of the Investigator's knowledge. Refer to Section 13 for further detail.
10. Record any device deficiencies. Refer to Section 13 for further detail.

12.1.3 1-Day Postoperative Visit (Visit 1/1A)

Visit 1: 1-2 Days Post 1st Eye Implantation, Monocular 1st Eye

Visit 1A: 1-2 Days Post 2nd Eye Implantation, Monocular 2nd Eye

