## **3 Subject Characteristics and Study Conduct Summaries**

Subject characteristics and study conduct summaries include tables and listings such as a subject disposition table, demographics and baseline characteristics tables (including age, gender, race, ethnicity), listing of treatment assignment by investigator, summary of screen failures by reason and listing of subjects excluded from key analysis sets including reasons. All descriptive summary statistics will be displayed with n and % for categorical data, and with mean, median, standard deviation, number of subjects, minimum, and maximum for continuous data. Tables will be presented by treatment and overall.

Subject characteristics and study conduct summaries will be presented for the primary effectiveness analysis set and the safety analysis set. Subject characteristics and study conduct summaries for the BAS analysis set will be presented if the number of subjects excluded exceeds 10%.

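### Does the best-case set need the bilateral-implantation condition, and does superiority need a run by randomised arm?

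*SAP*

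**What the plan says.** SAP 2.1 and Protocol 15.2 define two effectiveness sets in the same words. For the AAS: "The all-implanted analysis set (AAS) will include all eyes with successful test or control article bilateral implantation". For the BAS: "The best-case analysis set (BAS) will include all eyes successfully implanted with the test or control article that had at least one postoperative visit", followed by exclusions for macular degeneration, major protocol deviations and pregnancy. Neither document calls the BAS a subset of the AAS.

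The AAS is the main set for the six visual acuity tests, and the BAS is their sensitivity set (SAP Table 4-2). For two other outcomes the roles are reversed: "The BAS will be the primary set for binocular defocus and contrast sensitivity". SAP 3 adds that "Subject characteristics and study conduct summaries for the BAS analysis set will be presented if the number of subjects excluded exceeds 10" per cent.

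SAP 2.1 and Protocol 15.1 group subjects by the lens actually implanted. Table 4-2 gives each superiority test one AAS row and one BAS row, both on that basis.

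**The concern.** The main set asks for two study lenses and the set called best-case does not, although its endpoints are binocular and the model in SAP 4.3.1 takes the subject as its unit.

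The protocol contains a route to a one-lens subject. Protocol 10.3 lists surgical events that "prevent the study lens from being implanted. This is true for both eyes", and the eyes are operated on separately: "Visit 00A: 2-21 Days Post 1st Eye Implantation, Monocular 2nd Eye". The BAS visit condition can already be met before then: "Visit 1: 1-2 Days Post 1st Eye Implantation, Monocular 1st Eye". If the second eye is barred from the study lens, the subject leaves the AAS while the first eye still meets the BAS wording. Binocular results could then arrive through footnote 1 of the visit schedule: "If a subject exits early, the Visit 4A procedures should be performed at the last available visit, if at all possible".

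The by-eye wording also gives no explicit rule for a binocular score when macular degeneration affects one eye only, and the SAP 3 trigger counts subjects although the BAS is defined by eye.

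Separately, a superiority claim in a randomised trial is often checked by randomised arm, and Table 4-2 has no such row. At stake would be a sensitivity set that admits someone the main set excludes, and a superiority result that might depend on regrouping after randomisation.

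**Working it through.** **Inputs.** From SAP 7: SD 0.16 logMAR, 76 per arm, superiority difference 0.09. From SAP 4.2.1: margin 0.1. The documents give no rate of second-eye exclusion, no acuity deficit for a one-lens subject and no rate of wrong-lens implantation. I assume 1% to 3% second-eye exclusion (0.01 × 160 = 1.6 to 0.03 × 160 = 4.8 subjects over both arms) and a binocular score d = 0.2 to 0.3 logMAR worse.

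**The plan's own figures.** SE of the difference = 0.16 × √(2/76) = 0.02596. Non-inferiority power at one-sided 2.5% is 96.9% by the t distribution (97.1% normal), against the stated 98%. Superiority power at 0.09 is 93.1% by t, which agrees with the stated figure of over 90%. Neither is in dispute here.

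**Where a one-lens subject could enter**

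| Step | What the documents provide |
|---|---|
| Second eye barred from the study lens | Possible under Protocol 10.3 |
| First eye meets the BAS wording | Yes, unless the event counts as a major deviation, a term left undefined |
| Fellow eye meets the BAS wording | No, it carries no study lens |
| Scheduled binocular testing | Visits 3A and 4A only, both timed from second-eye implantation |
| Other binocular data | Early-exit footnote only, not guaranteed |
| Formal test affected | None; the main analysis of all six uses the AAS |
| Main BAS outcomes affected | Defocus and contrast sensitivity: no hypothesis test (SAP 4.2.2), repeated on the AAS (Table 4-2) |

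**Size if it happens.** With k such subjects added to one arm, the shift in that arm's mean is k × d/(76 + k).

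- k = 2, d = 0.2: 0.4/78 = 0.0051, or 0.0051/0.02596 = 0.20 SE.
- k = 2, d = 0.3: 0.6/78 = 0.0077, or 0.30 SE.
- One subject in each arm: the shifts cancel and the difference moves by about zero.

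*BAS sensitivity run of the primary test.* At an observed difference of zero, the upper 90% bound is t(0.95, 150) × SE = 1.655 × 0.02596 = 0.043. With two one-lens subjects in the test arm, and the pooled SD raised to 0.1616 (d = 0.2) or 0.1635 (d = 0.3) by the mixture, the SE is 0.0260 or 0.0264. The bound is 0.0051 + 1.655 × 0.0260 = 0.048, or 0.0077 + 1.655 × 0.0264 = 0.051. Both lie well below 0.1.

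*Defocus plot.* If the SD of 0.16 also held at a defocus step, which the documents do not say, the 90% half-width of one arm's mean is 1.665 × 0.16/√76 = 0.0306. The shift is 0.0051/0.0306 = 17% to 0.0077/0.0306 = 25% of that. For contrast sensitivity the documents give no SD, so no size can be computed.

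*SAP 3 trigger.* Suppose 17 of 160 AAS subjects are excluded from the BAS: 17/160 = 10.6%. Netting off two one-lens entrants would give 15/160 = 9.4%. Counting the subjects excluded, as SAP 3 words it, gives the first figure. The only consequence is whether a descriptive table is printed.

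**Grouping by randomised arm.** With w wrong-lens subjects in one arm and a true difference of 0.09, the two groupings differ by 0.09 × w/76. For w = 1 this is 0.0012. For w = 2 it is 0.0024 (0.0024/0.02596 = 0.09 SE), and power of the randomised-arm run falls from 93.1% to 91.8%. For w = 0 the two analyses are identical.

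**The case for a change.** The best case for a change is that the definitions do not nest, the repair is one sentence, and the usual safeguards are not written down. Withholding the lens under Protocol 10.3 complies with the protocol, so it is not obviously a major deviation. Protocol 10 addresses exclusion before first-eye surgery and is silent on the second eye. Protocol 15.1 settles evaluability before unmasking but states no criterion for one-eye cases. On superiority, both rows of Table 4-2 share the as-implanted grouping, so neither shows what regrouping does.

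The textual point stands: the bilateral condition appears in one definition and not in the other. What does not follow is that analysts would be misled. The BAS admits eyes. A binocular score from a one-lens subject rests partly on an eye outside the set, so leaving it out is the natural reading, and the same reasoning settles macular degeneration in one eye. The set's name and the SAP 3 count of excluded subjects point the same way, and the decision is taken under masking.

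On superiority, the as-implanted rule is stated openly and identically in both documents. A run by randomised arm confined to AAS subjects would still condition on successful bilateral implantation after randomisation, so it would detect little beyond a lens mix-up. Widening the population to avoid that would mix one-lens subjects into a comparison of bilateral implants.

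**Conclusion.** No change is needed. The BAS definition lacks a detail that masked evaluability review can supply in the obvious way, and its effect is confined to descriptive endpoints and sensitivity runs. Under the assumed inputs, two one-lens subjects in the same arm move the BAS difference by 0.005 to 0.008 logMAR and leave the upper bound of the primary comparison at 0.051 or below. The AAS results, which carry every decision, do not move at all. The missing randomised-arm run is a matter of preference and is worth 0.0012 logMAR per wrong-lens subject at a true difference of 0.09.

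This rests on the assumed 1% to 3% exclusion rate and 0.2 to 0.3 logMAR deficit, and on the planning SD of 0.16. A higher rate concentrated in one arm would make the BAS descriptive results less clean, but the parallel AAS results would show it. Since the plan as written already gives sound results, amending Protocol 15.2 would bring no gain in any conclusion.
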